# Statistical analysis:

The mean change from Randomization (Week 12) to Week 24 (Weeks 13,14,15,16,18,20, 22 and 24) in YGTSS-GS will be summarized. This endpoint will be analyzed with a Mixed Model for Repeated

This document is confidential.

SAP text Version: SAP text 3.0 6-Dec-2023

Controlled Document ID: 3903A.02, Effective Date 31-Aug-2020

Measures (MMRM) model using the SAS MIXED procedure with REPEATED statement. The model with an unstructured covariance matrix will include fixed effects for treatment, visit, interaction between treatment and visit, region, age group (0 = children 6-11, 1 = adolescents 12-17, 2=adults >=18) and covariate for week 12 YGTSS-GS. Visit will include weeks 13,14,15,16,18,20, 22 and 24. By visit comparisons will be provided. All observed endpoint data will be used in this analysis, without imputation.

Summary statistics will be presented along with a full data listing by treatment group.

10.2.7. Mean change from Randomization (Week 12) to Week 24 in the Caregiver Global Impression of Change (CaGI-C) for ecopipam compared to placebo.

The CaGI-C scale is an 8-point Likert scale for subjects < 18 years old that asks the caregiver the following question: overall, how have the patient's symptoms changed (if at all) since the beginning of the study (before starting treatment)? The CaGI-C is rated as follows: 0 (Not rated), 1 (very much improved), 2 (much improved), 3 (minimally improved), 4 (no change), 5 (minimally worse, 6 (much worse), and 7 (very much worse).

CaGI-C will be assessed at Weeks 4, 12, 18 and 24.

#### Derived Variables and Statistical analysis:

The mean change from Randomization (Week 12) to Week 24 (Weeks 18 and 24) in CaGI-C will be summarized. This endpoint will be analyzed with a Mixed Model for Repeated Measures (MMRM) model using the SAS MIXED procedure with REPEATED statement. The model with an unstructured covariance matrix will include fixed effects for treatment, visit, interaction between treatment and visit, region, age group (0 = children 6-11, 1 = adolescents 12-17) and covariate for week 12 CaGI-C. Visit will include weeks 18 and 24. By visit comparisons will be provided. In the event the model does not converge using the unstructured covariance matrix, the methods described in Section 10.2.4 will be tried. The final covariance structure will be documented in the table. All observed endpoint data will be used in this analysis, without imputation.

Summary statistics will be presented along with a full data listing by treatment group.

10.2.8. Time from Randomization (Week 12) to loss of ≥ 50% of the improvement from Baseline (Day 1) experienced on the YGTSS-TTS at the last visit (Week 12) in the open-label Stabilization period

# Statistical analysis:

An exploratory analysis will be performed on subjects with YGTSS-TTS. The analysis method will be similar to the primary efficacy analysis as described in Section 10.1. Data from subjects who complete or discontinue from the double-blind R/WD period without loss of  $\geq 50\%$  of the improvement will be considered as censored observations. The log rank test will be the primary test of statistical significance. Kaplan-Meier curves will be used to compare the times to loss of  $\geq 50\%$  of the improvement between the treatment groups. The hazard ratio and its 95% confidence interval (CI) will be estimated from the Cox proportional hazard model with treatment as a factor.

This document is confidential.

SAP text Version: SAP text 3.0 6-Dec-2023

Controlled Document ID: 3903A.02, Effective Date 31-Aug-2020

10.2.9. Mean change from Randomization (Week 12) to Week 24 in the Clinical Global Impression of Tourette Syndrome Improvement (CGI-TS-I) for ecopipam compared to placebo.

An exploratory analysis will be performed on the change in CGI-TS-I from randomization to Week 24.

#### Statistical analysis:

The mean change from Randomization (Week 12) to Week 24 (Weeks 13,14,15,16,18,20, 22 and 24) in CGI-TS-I will be summarized. This endpoint will be analyzed with a Mixed Model for Repeated Measures (MMRM) model using the SAS MIXED procedure with REPEATED statement. The model with an unstructured covariance matrix will include fixed effects for treatment, visit, interaction between treatment and visit, region, age group (0 = children 6-11, 1 = adolescents 12-17, 2=adults >=18) and covariate for week 12 CGI-TS-I. Visit will include weeks 13,14,15,16,18,20, 22 and 24. By visit comparisons will be provided. In the event the model does not converge using the unstructured covariance matrix, the methods described in Section 10.2.4 will be tried. The final covariance structure will be documented in the table. All observed endpoint data will be used in this analysis, without imputation.

Summary statistics will be presented along with a full data listing by treatment group.

10.2.10. Mean change from Randomization (Week 12) to Week 24 in the Premonitory Urge for Tics Scale (PUTS).

The PUTS is a 9-item self-report questionnaire measuring premonitory sensations in individuals with tics. In this study, the rater will read the questions to 6-17- year-old subjects and record their responses. Each item is scored from 1 (not at all true) to 4 (very much true). Thus, total scores range from 9 to 36, and higher scores represent greater premonitory urges, indicative of worst severity. An exploratory analysis will be performed on the change in PUTS score from randomization to Week 24.

# **Derived Variables and Statistical analysis:**

The total score is computed by summing the 9 items without imputing missing values. The score will be calculated only if all the questions are answered. Thus, total scores range from 9 to 36, and higher scores represent greater premonitory urges, indicative of worst severity. The mean change from Randomization (Week 12) to Week 24 (Weeks 18 and 24) in PUTS will be summarized. This endpoint will be analyzed with a Mixed Model for Repeated Measures (MMRM) model using the SAS MIXED procedure with REPEATED statement. The model with an unstructured covariance matrix will include fixed effects for treatment, visit, interaction between treatment and visit, region, age group (0 = children 6-11, 1 = adolescents 12-17) and covariate for week 12 PUTS. Visit will include weeks 18 and 24. By visit comparisons will be provided. In the event the model does not converge using the unstructured covariance matrix, the methods described in Section 10.2.4 will be tried. The final covariance structure will be documented in the table. All observed endpoint data will be used in this analysis, without imputation. Summary statistics will be presented along with a full data listing by treatment group.

10.2.11. Mean change from Baseline (Day 1) to Week 24 in Gilles de la Tourette Syndrome—Quality of Life Scale for Children and Adolescents (C&A-GTS-QOL) score for ecopipam compared to placebo.

Gilles de la Tourette Syndrome—Quality of Life Scale for Children and Adolescents (C&A-GTS-QOL) is a patient-reported health related quality of life measure developed for children and adolescents. The C&A-GTS-QOL is a 27-item questionnaire specific to TS patients that asks the patient to assess the extent to which their quality of life is impacted by their symptoms. The C&A-GTS-QOL contains 4 subscales (psychological, physical/activities of daily living (ADL), obsessive-compulsive, and cognitive) and uses a 5 point Likert scale ranging from no problem to extreme problem. Higher scores indicate worse symptom severity. The instrument includes a visual analogue scale used to express the extent of self-satisfaction about life. Higher scores indicate greater satisfaction. Patients will also be asked how satisfied they feel overall with their life at that moment by using a Visual Analogue Scale (VAS) scale between 0 and 100.

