^c If visits at Weeks 4, 8 and/or 12 are completed in locations other than study clinic due to restrictions because of the COVID-19 pandemic or other qualifying event, then collection of labs for PK assessments are optional.

f Week 2 and 30-Day FU visits will be a telephone call. If there are any abnormal findings, the subject will be brought to the site for full assessment. Subjects who complete the Baseline visit for the EBS-101-TD-391 open label extension study within 30 days of the Week 24 visit are not required to complete the 30-Day FU telephone call.

^g Administration applicable to adult subjects only.

^h Administration applicable to child and adolescent subjects only (6-17 years of age).

ⁱ For women of childbearing potential only. If positive, request a serum HCG on the Chemistry blood sample requisition form for confirmation of pregnancy.

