# 5.3. Exploratory Endpoints

- 1. Time from Randomization (Week 12) to a worsening by at least one category of the Global Impression Tourette's Syndrome of Severity (CGI-TS-S) in subjects ≥ 6 and < 18 years for ecopipam compared to those receiving placebo during the double-blind, R/WD period. If there is a strong correlation of this endpoint with Relapse criteria based on the YGTSS-TTS, it may be considered as a secondary endpoint with agreement from Health Authorities.
- 2. Time from Randomization (Week 12) to a worsening by at least one category of the CGI-TS-S in all subjects for ecopipam compared to those receiving placebo irrespective of age. If there is a strong correlation of this endpoint with Relapse criteria based on the YGTSS-TTS, it may be considered as a secondary endpoint with agreement from Health Authorities.
- 3. Mean change from Randomization (Week 12) to Week 24 in the YGTSS-TTS for ecopipam compared to placebo.
- 4. Mean change from Randomization (Week 12) to Week 24 in the CGI-TS-S for ecopipam compared to placebo.
- 5. Mean change from Randomization (Week 12) to Week 24 in the YGTSS-Global Severity (GS) Score for ecopipam compared to placebo.
- 6. Mean change from Randomization (Week 12) to Week 24 in the Caregiver Global Impression of Change (CaGI-C) for ecopipam compared to placebo.
- Time from Randomization (Week 12) to a loss of ≥ 50% of the improvement from Baseline (Day 1) experienced on the YGTSS-TTS at the last visit (Week 12) in the open-label Stabilization period.
- 8. Mean change from Randomization (Week 12) to Week 24 in the Clinical Global Impression of Tourette Syndrome Improvement (CGI-TS-I) for ecopipam compared to placebo.
- 9. Mean change from Randomization (Week 12) to Week 24 in the Premonitory Urge for Tics Scale (PUTS) for ecopipam compared to placebo.
- Mean change from Baseline (Day 1) to Week 24 in Gilles de la Tourette Syndrome

  —Quality of
  Life Scale for Children and Adolescents (C&A-GTS-QOL) score for ecopipam compared to
  placebo.
- 11. Mean change from Baseline (Day 1) to Week 24 in Gilles de la Tourette Syndrome–Quality of Life Scale (GTS-QOL) score in adults for ecopipam compared to placebo.

This document is confidential.

SAP text Version: SAP text 3.0 6-Dec-2023

Controlled Document ID: 3903A.02, Effective Date 31-Aug-2020

- 12. Mean change from Baseline (Day 1) to Week 12 in the YGTSS-TTS.

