The mean change from Randomization (Week 12) to Week 24 (Weeks 13,14,15,16,18,20, 22 and 24) in YGTSS-TTS will be summarized. This endpoint will be analyzed with a Mixed Model for Repeated Measures (MMRM) model using the SAS MIXED procedure with REPEATED statement. The model with an unstructured covariance matrix will include fixed effects for treatment, visit, interaction between treatment and visit, region, age group (0 = children 6-11, 1 = adolescents 12-17, 2=adults >=18) and covariate for week 12 YGTSS-TTS. Visit will include weeks 13,14,15,16,18, 20, 22 and 24. By visit comparisons will be provided. In the event the model does not converge using the standard unstructured covariance matrix, the Fisher scoring algorithm to obtain initial values of covariance parameters will be tried. If this method fails to converge, the FA0(T) structure will be tried. Following failure of this method, the successive univariate method proposed by Lu and Mehrotra (2010) will be tried. In the event all the previous methods fail to converge, the autoregressive and Toeplitz structures will be tried, and a sandwich estimator for the treatment effect estimate will be implemented. The final covariance structure will be documented in the table. All observed endpoint data will be used in this analysis, without imputation.

Summary statistics will be presented along with a full data listing by treatment group.

10.2.5. Mean change from Randomization (Week 12) to Week 24 in the CGI-TS-S for ecopipam compared to placebo.

An exploratory analysis will be performed on the change in CGI-TS-S from randomization to Week 24.

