#### Statistical analysis:

The VAS, subscales and total score will be analyzed with a fixed effects model using the SAS MIXED procedure. The model will include fixed effects for treatment, region, and covariate for baseline C&A-GTS-QOL. All observed endpoint data will be used in this analysis.

Summary statistics for the VAS, subscales, and total score will be presented along with a full data listing by treatment group.

10.2.13. Mean change from Baseline (Day 1) to Week 12 in the YGTSS-TTS.

See section 10.1 for a description of the YGTSS-TTS. An exploratory analysis will be performed on the change in YGTSS-TTS from Baseline to Week 12.

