Caregiver Global Impression of Change h				X		X					X			X			
Gilles de la Tourette Syndrome – Quality of Life Scale for Children and Adolescentsh		X				X								X			
Gilles de la Tourette Syndrome – Quality of Life Scale g		X				X								X			

This document is confidential.

SAP text Version: SAP text 3.0 6-Dec-2023 Controlled Document ID: **3903A.02**, Effective Date 31-Aug-2020 Filing requirements: TMF

		Open-Label Stabilization Period															
	Screening Period a								Safety Follow-Up (Days 170-199)								
Visit/TC Study Day	Screening VISIT 1 Day -28 to -1	Baseline VISIT 2 Day 1	W 2 f Day 15 Telephone call only (±3d)	W4 / VISIT 3/ Day 29 (±3d)	W8 / VISIT 4 / Day 57 (±3d)	W 12 VISIT 5 Day 85 (±3d)	W13 / VISIT 6 / Day 92 (±3d)	W14 / VISIT 7 / Day 99 (±3d)	W15 / VISIT 8 / Day 106 (±3d)	W16 / VISIT 9 / Day 113 (±3d)	W18 / VISIT 10 / Day 127 (±3d)	W20 / VISIT 11 / Day 141 (±3d)	W22 / VISIT 12/ Day 155 (±3d)	W 24 VISIT 13 Day 169 or Relapse or ET (±3d)	7 Day F/U VISIT 14 (±3d)	14 Day F/U VISIT 15 (±3d)	30 Day F/U f Telephone call only (±3d)
Premonitory Urge for Tics Scale		X		X		X					X			X			
Columbia Suicide Severity Rating Scale	X	X	X	X	X	X	X	X	X	X	X	X	X	X	X	X	
Children's Depression Rating Scale – Revised h	X	X		X	X	X	X	X	X	X		X		X			
Pediatric Anxiety Rating Scale h		X		X	X	X	X	X	X	X		X		X			
Extrapyramidal Symptom Rating Scale		X		X	X	X	X	X	Х	X	X	X	X	X			
Swanson, Nolan, and Pelham Questionnaire-IV- 26 h		Х		X	Х	X	X	X	X	X		X		X			
Children's Yale- Brown Obsessive Compulsive Scale- II h		X		Х	X	X	X	X	Х	X		X		Х			
Patient Health Questionnaire-9g	X	X		X	X	X	X	X	X	X		X		X			

This document is confidential.

SAP text Version: SAP text 3.0 6-Dec-2023 Controlled Document ID: **3903A.02**, Effective Date 31-Aug-2020 Filing requirements: TMF

			Open-Label	Stabilizatio	on Period												
	Screening Period a			W	faintenance Phase Weeks 4 to 12 Day 29 up to 84)		Double-Blind Randomized Withdrawal Period Weeks 12 to 24 (Days 85 to 169)								Safety Follow-Up (Days 170-199)		

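### The adult GTS-QOL model adjusts for a child scale that adults never complete, and the PUTS model has no adult age level although the schedule implies that adults complete PUTS

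*SAP*

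**What the plan says.** **Adult GTS-QOL (SAP 10.2.12).** The endpoint is change from Baseline to Week 24 in adults. The VAS, the subscales and the total score are each to be modelled with "fixed effects for treatment, region, and covariate for baseline", and the scale named immediately after those words is the C&A-GTS-QOL. In Protocol Table 3 and SAP 16.1 that scale carries footnote h: "Administration applicable to child and adolescent subjects only (6-17 years of age". The GTS-QOL row carries footnote g: "Administration applicable to adult subjects only". Protocol 11.3.4 and 11.3.5 say that 18-year-olds count as adults and take the adult version.

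**PUTS (SAP 10.2.10).** The endpoint in SAP 5.3 is "Mean change from Randomization (Week 12) to Week 24 in the Premonitory Urge for Tics Scale (PUTS) for ecopipam compared to placebo", with no age limit. The model has "age group (0 = children 6-11, 1 = adolescents 12-17) and covariate for week 12 PUTS". The schedule row, "Premonitory Urge for Tics Scale", carries neither footnote g nor footnote h in either document. Protocol 11.3.3 describes PUTS as a self-report scale and adds that, in this study, the rater reads the items to subjects aged 6 to 17. SAP 10.2.10 also says that all observed data enter the analysis without imputation.

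**The three-level version.** SAP 10.2.4 uses "age group (0 = children 6-11, 1 = adolescents 12-17, 2=adults >=18) and covariate for week 12 YGTSS-TTS". The section just before PUTS, 10.2.9, uses "age group (0 = children 6-11, 1 = adolescents 12-17, 2=adults >=18) and covariate for week 12 CGI-TS-I".

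**The concern.** Each model, taken as written, leaves out adults. In 10.2.12 the covariate does not exist for anyone in the target population. In 10.2.10 an adult falls outside the age coding. PROC MIXED excludes any record with a missing class or covariate value, so literal programming would give no adult GTS-QOL model and a PUTS model on minors alone.

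Evaluating maintenance of efficacy in adults is a secondary objective (SAP 3.2), and GTS-QOL is the only efficacy endpoint defined for adults alone. If the text stays as it is, the programmer has to decide who is in the PUTS analysis and what the GTS-QOL covariate is. A correction made after unblinding would be a post hoc change to a pre-specified analysis.

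**Working it through.** The plan gives no figure to reproduce. The check sets the sections side by side and then sizes the group affected.

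**1. GTS-QOL.** The outcome is given only to adults (footnote g) and the covariate only to ages 6 to 17 (footnote h). Protocol Section 11 fixes the instrument by age at informed consent and does not change it later, so nobody moves from one scale to the other during the study. No subject can have both the outcome and the covariate, and the number of usable records is 0. Section 10.2.11 uses the same covariate, correctly, for the child scale. The text in 10.2.12 was probably carried over from there.

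**2. PUTS: which models use which coding.**

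| Age coding | SAP sections | Scale population |
|---|---|---|
| Three levels | 10.2.4, 10.2.5, 10.2.6, 10.2.9, 10.2.15, 10.2.16, 10.2.17, 10.2.23, 10.2.24 | YGTSS and CGI-TS scales, all ages |
| Two levels | 10.2.7 (CaGI-C), 10.2.11 and 10.2.19 (C&A-GTS-QOL) | Marked h in the schedule, under 18 only |
| Two levels | 10.2.10 (PUTS) | No age mark in the schedule |

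PUTS is the only two-level model whose scale is not marked as paediatric.

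**3. PUTS: what the missing footnote implies.** The other rating-scale rows with neither g nor h are YGTSS, CGI-TS-S, CGI-TS-I, C-SSRS and ESRS. Protocol 11.1.1 describes YGTSS for children and adults, Protocol 11.3.1 provides paediatric and adult CGI-TS versions, and SAP Section 12 gives C-SSRS and ESRS to all age groups. An unmarked row therefore means all ages wherever this can be checked. The sentence about reading items aloud to ages 6 to 17 sets how minors complete a self-report scale. It does not exclude adults.

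**4. Size.** Inputs:
- about 40 adults enrolled (SAP 4.3);
- 98 children and adolescents randomized (SAP 4.3);
- a 50% open-label response rate, which SAP 4.3 states for children and adolescents only.

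Using a response rate *r* for adults is an assumption. Adults randomized = 40 × *r*, and their share = 40*r* / (98 + 40*r*).

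| Assumed adult response | Adults randomized | Share of all randomized |
|---|---|---|
| 30% | 40 × 0.3 = 12 | 12/110 = 11% |
| 50% | 40 × 0.5 = 20 | 20/118 = 17% |
| 70% | 40 × 0.7 = 28 | 28/126 = 22% |

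These are the adults that literal coding would remove from the PUTS model, if adults do complete PUTS. They are also the adults that the GTS-QOL model could use once its covariate is corrected, less any with missing scores.

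**The case against.** **PUTS.** The strongest reply is that adult completion is inferred. No sentence says that adults complete PUTS. The only ages named in its description are 6 to 17, and the two-level coding matches them. An endpoint without an age limit proves little: the CaGI-C endpoint has none either, yet that scale is for subjects under 18. The adult subgroup plan in SAP 8.6 is worded for all efficacy endpoints, which would include CaGI-C, so it cannot settle the matter alone. The missing footnote could itself be the mistake. All of this stands. It means that the intended PUTS population is unresolved, and it does not make the documents consistent.

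It can also be said that adults need not be lost. The parenthesis may be only a coding key, and the SAP's sample code for the YGTSS-TTS imputation uses a single age-group variable. If that variable carries the adult code 2, adults enter the model, in line with the instruction to use all observed data. This also stands: the loss follows only if the coding is applied literally.

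**GTS-QOL.** The slip is obvious, and a programmer would probably correct it. That is likely, but the specified model would then not be the one that is run.

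**Stronger readings.** A reader might infer that the PUTS result would be paediatric-only while labelled as covering everyone. The SAP contains no such label, and it requires summary statistics and a full listing by treatment group. A reader might also infer that the adults would have almost no other output. SAP 8.6 plans adult subgroup analyses, and SAP 12.7 summarises four adult-only safety scales.

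**Conclusion.** The GTS-QOL covariate is wrong as written. This follows from the text without assumptions: no adult has a baseline C&A-GTS-QOL, so the model cannot be fitted.

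The PUTS model conflicts with the schedule and sits badly with the adult subgroup plan. The evidence favours adult completion, but the documents do not state it. The conclusion is that the two places must be reconciled. It would go too far to say that adult PUTS data will certainly be lost.

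About 20 of 118 randomized subjects (17%) are affected if adults respond at the paediatric rate of 50%. The range is 12 to 28 adults (11% to 22%) at an assumed 30% to 70%. These figures also rest on the planned 40 adults and 98 minors.

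The consequence is limited. Both endpoints are exploratory and outside the fixed testing sequence in SAP 10.2, and the primary analysis concerns subjects under 18. Nobody should read this as a threat to a confirmatory test, to alpha or to the sample size.

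**What to change.** - **SAP 10.2.12:** replace the covariate with the baseline GTS-QOL score that matches the outcome being modelled: VAS for VAS, each subscale for itself, total for total.
- **SAP 10.2.10:** first settle whether adults complete PUTS. If they do, add the level `2=adults >=18`, as in 10.2.4. If PUTS is meant for ages 6 to 17 only, say so in the endpoint and the analysis text, and put footnote h on the PUTS row in Protocol Table 3 and SAP 16.1.

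The GTS-QOL change is a few words and costs nothing. The PUTS change is equally short but needs the decision first: adding an adult level to a scale meant only for minors would change the stated analysis population. Both edits should be made before unblinding.

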#### **Derived Variables and Statistical Analysis:**

Following are the questions assessed in each C&A GTS QOL subscale:

- Psychological (questions 16, 17, 18, 19, 20, 21, 22, 23, 24, 25, 27)
- Physical/ADL (questions 1, 2, 3, 4, 5, 6, 26)
- Obsessive-compulsive (questions 7, 8, 9, 10,15)
- Cognitive (questions 11, 12, 13, 14)

Scores for the four subscales are generated by summing items and, for ease of interpretation, transformation to a range of 0 to 100 (100x [(observed score - min possible score)/ (max possible score - min possible score)]). The total score, resulting from the sum of the subscale scores, is also normalized to a 0–100 range. If a response to at least 1 question within subscale is missing, then the missing responses will not be replaced, and the subscale score will be set to missing; if at least 1 subscale is missing then the total score will be set to missing. For all analysis and summary, transformed scores will be used.

An exploratory analysis will be performed on the change in C&A-GTS-QOL total score and VAS from Baseline to Week 24.

The mean change from Baseline (Day 1) to Week 24 in C&A-GTS-QOL will be summarized. The VAS, subscales and total score will be analyzed with a fixed effects model using the SAS MIXED procedure. The model will include fixed effects for treatment, region, age group (0 = children 6-11, 1 = adolescents 12-17) and covariate for baseline C&A-GTS-QOL. All observed endpoint data will be used in this analysis.

Summary statistics for the VAS, subscales, and total score will be presented along with a full data listing by treatment group.

10.2.12. Mean change from Baseline (Day 1) to Week 24 in Gilles de la Tourette Syndrome—Quality of Life Scale (GTS-QOL) score in adults for ecopipam compared to placebo.

See section 10.2.11 for a description of the Gilles de la Tourette Syndrome–Quality of Life Scale (GTS-QOL). An exploratory analysis will be performed on the change in GTS-QOL VAS and total score from Baseline to Week 24.

